### Exclusion Criteria

1. Active infection or wound complication at implant site.
2. Significant psychiatric comorbidity (e.g. uncontrolled depression, psychosis).
3. Planned surgery, stimulation adjustments, or medication changes within 2 weeks prior to enrolment or at any time during the study period.
4. Pregnancy or breastfeeding.
5. Occurrence of any adverse event during the study that meets the predefined withdrawal criteria (see Safety Monitoring); such participants are withdrawn immediately and not re-randomized.

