## Study Schedule & Assessments

Study Day	Activity
-7 to -1	Screening, informed consent, baseline questionnaires, recording perception threshold.
0	Randomization; begin first 24 h wash-out (device OFF).
1-5	Period 1 treatment (Active or Sham) + twice-daily electronic diary.
5	24 h wash-out (device OFF).
6-10	Period 2 treatment + diaries.
10	End-of-study visit, adverse event review, exit interview

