## Statistical Analysis Plan

- Sample Size – Assuming within-subject SD = 1.5 NRS points, minimally important difference = 1 point,  $\alpha = 0.05$ , power = 0.90, two-sided paired test → 24 completers needed (calculated with G\*Power). To accommodate 15 % attrition, target enrolment = 28.
- Primary Analysis – Paired t-test (or Wilcoxon signed-rank if non-normal) comparing mean NRS pain across days 3–5 between Active and Sham periods. If a period is aborted due to high pain, the last recorded score will be carried forward for the remaining days. Treatment order and carry-over tested via mixed-effects model with fixed effects for treatment, period, and sequence.
- Secondary Outcomes – Similar within-subject comparisons; Bonferroni correction applied.
- Missing Data – Multiple imputation if > 5 % diary fields missing.

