## Safety Monitoring

All adverse events (AEs) occurring between screening and study exit lead to the immediate withdrawal of the participant from the trial. If the AE is judged related to either the DRG stimulation or the sham condition, it is captured in the study database with these mandatory details: (i) AE type and MedDRA term, (ii) date/time of onset, (iii) action taken (e.g., device OFF, medical treatment), and (iv) final outcome/resolution.

The event report is recorded in Patientkollen within 24 h via the SAE portal and automatically forwarded to the Data Safety Monitoring Board (DSMB) for review at its next meeting.

**Intraperiod stopping rule:** If any diary entry records (i) an NRS pain score > 8 or (ii) an increase  $\geq 4$  points versus Baseline Day 0, the current treatment period is halted. The

participant immediately enters the 24 h wash-out and then crosses to the alternate arm. The episode is logged as an AE (device insufficient efficacy) and triggers a real-time alert to the DSMB.

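### Safety Monitoring both withdraws and crosses over a participant stopped for high pain, and no exemption is stated

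*Combined protocol and SAP*

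**What the plan says.** Safety Monitoring opens with a general rule: "All adverse events (AEs) occurring between screening and study exit lead to the immediate withdrawal of the participant from the trial". The stopping rule in the same section applies when a diary score is above 8 or has risen by at least 4; its wording on the rise ends: "points versus Baseline Day 0, the current treatment period is halted". It does not end participation, since under it a stopped "participant immediately enters the 24 h wash-out and then crosses to the alternate arm". The rule then classifies the event: "The episode is logged as an AE (device insufficient efficacy) and triggers a real-time alert to the DSMB".

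Three other places bear on the conflict:

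- **Exclusion Criteria, item 5** covers "Occurrence of any adverse event during the study that meets the predefined withdrawal criteria (see Safety Monitoring" and requires those participants to be removed at once. It points back to Safety Monitoring and defines no subset of events itself.
- **Statistical Analysis Plan**, primary analysis: "If a period is aborted due to high pain, the last recorded score will be carried forward for the remaining days".
- **Randomisation & Blinding Procedures** withdraws a participant when the device access code is disclosed in an emergency. That is a separate route, triggered by disclosure and not by a diary score.

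The baseline for the 4-point rise is only partly defined. Study Schedule & Assessments lists, for days -7 to -1, "Screening, informed consent, baseline questionnaires, recording perception threshold", and for Day 0, "Randomization; begin first 24 h wash-out (device OFF".

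**The concern.** A pain stop is by the plan's own classification an adverse event, and every adverse event requires withdrawal. The stopping rule nevertheless keeps the participant in the trial. Staff who receive a qualifying diary entry can follow either sentence and be compliant with one and in breach of the other, so identical events may be handled differently.

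The choice reaches the primary analysis, which is a paired comparison. A participant withdrawn during Period 1 has no second period and contributes no pair. The loss would depend on outcome: participants are established responders and Sham is the device switched off, so stops can be expected more often on Sham. The trial has little slack to absorb such losses.

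**Working it through.** **1. The instructions side by side, for one qualifying diary entry**

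| Source | Instruction |
|---|---|
| Safety Monitoring, opening sentence | Withdraw (any adverse event) |
| Safety Monitoring, stopping rule | Halt the period, wash out, cross over; log as adverse event |
| Exclusion Criteria, item 5 | Withdraw if criteria are met; criteria are those in Safety Monitoring |
| Statistical Analysis Plan | Carry the last score forward in the aborted period |

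The only adverse-event criterion in Safety Monitoring is that all of them count, so item 5 does not resolve the conflict. The carry-forward rule implies that the participant stays, but it is an analysis rule. It could equally serve a Period 2 stop followed by withdrawal.

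**2. Which stops lose a pair if withdrawal is followed**

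- Period 1, on Sham or on Active: no second period, so the pair is lost.
- Period 2, on Sham or on Active: Period 1 is complete and carry-forward can fill the aborted period, so the pair need not be lost.

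**3. The plan's sample size**

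Inputs from the Statistical Analysis Plan: SD 1.5 (read as the SD of paired differences), difference 1, two-sided alpha 0.05, power 0.90.

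n = [1.5 × (1.960 + 1.282) / 1]² = 4.863² = 23.6, so 24, as stated.

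The exact paired-t calculation gives power 87.8 % with 24 pairs, 90.4 % with 26 and 92.5 % with 28. The margin is 28 − 24 = 4. The 15 % attrition allowance already uses it: 28 × 0.85 = 23.8.

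**4. Period 1 stops on Sham, if withdrawn**

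With 1:1 allocation, 14 of 28 are Sham-first. The stop rate p is an assumption. X ~ Binomial(14, p), expected losses = 14p, and P(X > 4) = 1 − Σ(k = 0 to 4) C(14,k) p^k (1−p)^(14−k).

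| p | Expected losses | P(more than 4) |
|---|---|---|
| 10 % | 1.4 | 0.9 % |
| 20 % | 2.8 | 13 % |
| 30 % | 4.2 | 42 % |

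This counts no other attrition and no Period 1 stops on Active.

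**5. Simulation of both readings**

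Assumptions:

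- 27 scenarios of 1,500 trials each; 28 participants, 14 per sequence; no other attrition; no time trend.
- Active mean pain 2.5, 3.0 or 3.5 (SD 1.5); true Sham minus Active 1.0; SD of differences 1.5.
- Diary noise SD 0.5, 0.8 or 1.1; 10 diaries per period; scores rounded and limited to 0–10.
- Baseline is one noisy score centred on the Active level, midway, or on the OFF level.
- Stops can occur on either treatment; paired t-test on days 3–5.

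Without any stopping the estimate is 0.98–1.02 and power 93–96 %. Active stops are 0–10 %.

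| Baseline at | Sham stops | Withdraw Period 1 stops: pairs | estimate | power | Cross over with carry-forward (28 pairs): estimate | power |
|---|---|---|---|---|---|---|
| Active level | 14–36 % | 21.6–26.0 | 0.88–0.97 | 67–88 % | 1.08–1.28 | 91–96 % |
| Midway | 3–26 % | 23.3–27.6 | 0.96–1.03 | 78–94 % | 1.04–1.23 | 90–95 % |
| OFF level | 2–20 % | 24.1–27.6 | 0.95–1.06 | 84.5–94.5 % | 1.01–1.15 | 88–95 % |

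Carry-forward inflates the estimate because 58–80 % of simulated Sham stops fall before Day 3. For these the days 3–5 mean is the trigger score alone. Replacing it with the mean of the scores observed in that period gives 1.04–1.14, 1.03–1.11 and 1.00–1.08 for the three baselines, with power 91–96 %.

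**The case against.** The best defence is that the intention is clear enough. The stopping rule is specific, follows the general sentence in the same section and sets out exact steps. The Statistical Analysis Plan has a matching rule for a period ended by high pain. Item 5 of the Exclusion Criteria speaks of criteria to be met, which would be redundant if every event qualified. On that reading this is a drafting omission, and the losses in power arise only if staff follow the less plausible sentence. This stands as to intention. It does not remove the conflict, because the word all leaves no room for an implied exception and nothing tells site staff which sentence governs.

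A reader might infer that following the withdrawal sentence would bias the trial towards no effect. The documents do not support that. In the simulation the estimate falls below 1.0 throughout only with an Active-level baseline; with the other two it lies on both sides. The plan names a Day 0 baseline and also begins device-OFF wash-out that day, so the text does not favour the Active-level case, although a score taken before switch-off remains possible.

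A reader might also infer that crossover is the less biased route. Under the same assumptions withdrawal shifts the estimate by −12 % to +6 %, while crossover with carry-forward raises it by 1–28 %, in favour of the therapy. That objection stands: the argument for the exemption is retention and power, not less bias.

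**Conclusion.** The contradiction is certain and rests on the text alone. What follows if the withdrawal sentence is applied is the loss of every Period 1 stop from a paired test whose margin of 4 is already allotted to ordinary attrition. This can cost power: under the stated assumptions it is 67–88 % with an Active-level baseline, but 84.5–94.5 % with an OFF-level baseline, where little is lost. All these figures depend on assumed stop rates, pain levels, diary noise and baseline state. The loss is tied to outcome, yet neither the size nor the direction of any bias is established. The point should be corrected before enrolment, since the analysis is to run from pre-specified scripts once the data are locked. It is not a reason to doubt the design.

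**What to change.** In Safety Monitoring and in item 5 of the Exclusion Criteria, state that a stopping-rule event is logged as an adverse event but is exempt from withdrawal for adverse events, and that:

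- after a Period 1 stop, the participant goes through wash-out and crosses over;
- after a Period 2 stop, the participant ends treatment and attends the end-of-study visit;
- in both cases, both periods enter the primary analysis under the Statistical Analysis Plan;
- these participants are withdrawn only at their own request, on the investigator's safety judgement, or when the access code is disclosed.

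In the Statistical Analysis Plan, add a sensitivity analysis that does not carry the trigger score forward. One option is the mean of the scores observed in the aborted period, using days 3–5 if any exist and otherwise all scores of that period.

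The cost is a short exemption and one extra analysis. There are two downsides. A participant stopped on Active in Period 1 then faces a device-OFF period, so the right to withdraw must be explicit. The sensitivity analysis reduces the carry-forward inflation, from 8–28 % to 4–14 % with an Active-level baseline and from 1–15 % to 0–8 % with an OFF-level baseline. It does not remove it, because the trigger score is still among those averaged and early stops rely on scores from before Day 3. The exemption also leaves the withdrawal rule for all other adverse events as it is.

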## Ethical Considerations

The study complies with the Declaration of Helsinki, ISO 14155 Good Clinical Practice, and Swedish regulations for medical-device research. Ethical approval has been obtained for this study from the Swedish Ethical Review Authority (Etikprövningsmyndigheten), DNR 2025-04065-01. It will be prospectively registered on the public registry ClinicalTrials.gov (identifier to be obtained) prior to enrolment of the first participant. All participants provide written informed e-consent via Patientkollen. Risks are minimal and relate mainly to temporary cessation of therapeutic stimulation.

## Dissemination

Results will be submitted to peer-reviewed journals and presented at pain and neuromodulation conferences. De-identified data and statistical code will be made available via an open repository (OSF) within 12 months of publication.

## Appendix 1: Data report from our quality database for patients with DRG stimulation therapy
